#### 9.1.2. Sensitivity Analysis

Two sensitivity analyses will be performed. The first sensitivity analysis will repeat the primary analysis counting both confirmed and unconfirmed relapses.

The second sensitivity analysis will use a negative binomial regression model, instead of the Poisson regression model, to compare relapse rates. The same covariates and offset term will be used as specified in the primary analysis. This model will be run twice: once repeating the primary analysis (confirmed relapses only) and once repeating the first sensitivity analysis (confirmed + unconfirmed relapses).

In addition to the specified sensitivity analyses, a Kaplan-Meier analysis on the difference in time to first confirmed relapse curves will also be performed. The estimated median time to first confirmed relapse will be reported, along with the associated 95% CI and log-rank p-values. A Kaplan-Meier plot will also be produced.

## 9.2. Key Secondary Efficacy Endpoints

The key secondary efficacy endpoints (rank ordered) are:

- 1. The number of new or enlarging hyperintense T2-weighted brain MRI lesions over 24 months
- 2. The number of GdE brain MRI lesions at Month 24
- 3. Time to onset of disability progression as defined by a sustained worsening in EDSS score of 1.0 points or more, confirmed after 3 months and after 6 months

#### 9.2.1. Analysis

# **Key Secondary Endpoint: The number of new or enlarging hyperintense T2-weighted brain MRI lesions over 24 months**

The primary analysis of the number of new or enlarging T2 hyperintense lesions over 24 months will be performed using a negative binomial regression model adjusted for region, age at Baseline, and Baseline number of GdE lesions, and will include the natural log transformation of the number of available MRI scans as an offset term. The odds ratios and their associated 95% CIs, relative reductions, and p-values will be reported.

The analysis will be repeated in each of the pre-specified subgroups shown in section 5. Forest plots showing the odds ratios and 95% CIs for the overall result and the results in each subgroup will be constructed.

Three sensitivity analyses will be performed: the first will repeat the primary T2 analysis using the mean number of T2 lesions from patients from the same treatment group to impute missing T2 values. The second will repeat the primary T2 analysis using last observation carried forward (LOCF) method for imputing missing T2 data values. Only data from post-Baseline MRI scans can be carried forward to subsequent timepoints for this analysis. The third will repeat the primary T2 analysis using only patients with complete T2 data at the relevant MRI visits (observed cases analysis). All three sensitivity analyses will include the natural log transformation of exposure time on study (instead of the number of available MRI scans) as the offset term.

All T2 lesion results will be listed.

#### Key Secondary Endpoint: The number of GdE brain MRI lesions at Month 24

The number of GdE brain MRI lesions at Month 24 will be analyzed using a negative binomial regression model adjusted for region, age at Baseline, and Baseline number of GdE lesions, and will include the natural log transformation of the number of available MRI scans as an offset term. The odds ratios and their associated 95% CIs, relative reductions, and p-values will be reported.

The analysis will be repeated in each of the pre-specified subgroups shown in section 5. Forest plots showing the odds ratios and 95% CIs for the overall result and the results in each subgroup will be constructed.

Three sensitivity analyses will be performed: the first will repeat the primary GdE analysis using the mean number of GdE lesions from patients from the same treatment group to impute missing GdE values. The second will repeat the primary GdE analysis using last observation carried forward (LOCF) method for imputing missing GdE data

values. Only data from post-Baseline MRI scans can be carried forward to the Month 24 timepoint for this analysis. The third will repeat the primary GdE analysis using only patients with complete GdE data at Month 24 (observed cases analysis). All three sensitivity analyses will include the natural log transformation of exposure time on study (instead of the number of available MRI scans) as the offset term.

All GdE lesion results will be listed

Key Secondary Endpoint: Time to onset of disability progression as defined by a sustained worsening in EDSS of 1.0 points or more, confirmed after 3 months and after 6 months

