#### 5.4.3. Visit Windows

A visit window method will be applied to determine visits across the study for MRI efficacy parameters and for the minimum times to confirmation of disability progressions. For MRI parameters, if a patient has multiple assessments within a visit window the value closest to the target day for that visit will be selected. If there are two values which are equidistant in terms of time then the later value will be selected. For disability progressions, a minimum length of time since the start of the progression is defined, based on the low end of the MRI visit window specifications.

The following visit windows are defined for MRI parameters:

Visit	Target Day	Window
Month 6	180	166 - 194
Month 12	360	346 - 374
Month 18	540	526 – 554
Month 24	720	706 - 734

The following minimum times are defined for disability progression confirmations:

- 3 month confirmation:  $\geq$  76 days after start of progression
- 6 month confirmation: ≥ 166 days after start of progression

For all efficacy and safety parameters, the last available assessment will be derived as the last value on treatment, whether scheduled or unscheduled.

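### The Month 24 GdE model offsets a one-scan count by the number of scans, and the imputed GdE and mean-imputed T2 sensitivity analyses offset values completed to Month 24 by a dropout's shorter time on study

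*SAP*

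**What the plan says.** SAP 9.2.1 uses the same sentence for the first two key secondary endpoints. Each model is adjusted for region, age and "Baseline number of GdE lesions, and will include the natural log transformation of the number of available MRI scans as an offset term". The first endpoint is a count of new or enlarging T2 lesions over 24 months. The second is a count at one time point: "The number of GdE brain MRI lesions at Month 24 will be analyzed using a negative binomial regression model".

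SAP 5.4.3 takes one scan per visit window; where there are several, "the value closest to the target day for that visit will be selected". Protocol Table 3 schedules Part B brain MRI at screening, Month 12 and Month 24 (footnote 10: yearly).

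Each endpoint has three sensitivity analyses: arm-mean imputation, LOCF and observed cases. All of them, for both endpoints, "will include the natural log transformation of exposure time on study (instead of the number of available MRI scans) as the offset term". For GdE LOCF, "Only data from post-Baseline MRI scans can be carried forward to the Month 24 timepoint for this analysis". The first T2 analysis works by "using the mean number of T2 lesions from patients from the same treatment group to impute missing T2 values". For T2 LOCF, "Only data from post-Baseline MRI scans can be carried forward to subsequent timepoints for this analysis", without saying whether the cumulative count or the count per interval is carried.

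The protocol (synopsis statistical methods for Part B, and 13.6.4) names the negative binomial model and its covariates but no offset. The SAP reports the results of both lesion models as odds ratios.

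**The concern.** A log offset turns a count into a rate, so the offset must measure the exposure over which the count was collected. Two parts of SAP 9.2.1 break that link.

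1. **Main GdE model.** The outcome is read from one scan, but the exposure is one or two scans (two or three if the baseline scan counts). Two patients with the same Month 24 count enter with rates differing by a factor of two because one of them missed Month 12.
2. **Imputed sensitivity analyses.** Mean-imputed GdE, LOCF GdE and mean-imputed T2 give an early leaver a value completed to Month 24, then divide by the time that patient actually stayed. Someone who left at 6 months is read at 24/6 = 4 times the rate.

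In both cases the arm with fewer scans or shorter follow-up has its rate inflated. GdE at Month 24 is second in the type 1 error-controlled sequence (SAP section 5), so its estimate should not depend on whether another scan was done. The imputed analyses are there to test robustness to missing data, yet their offset turns unequal dropout into an apparent treatment difference.

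**Working it through.** **Inputs.** The documents give no expected value for either lesion model, so there is no planned figure to reproduce. They give overall dropout only: 17% (protocol 13.2) and about 12% (SAP 5.1). Missingness by arm, lesion means, dispersion and dropout timing are therefore assumptions. Percentages below are IFN β-1a / RPC1063, and ratios are RPC1063 over IFN β-1a with no true effect.

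**Main GdE model: bounds by hand.** Let p be the share missing the Month 12 scan among patients who have a Month 24 count. A negative binomial fit lies between two limits:

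- Little dispersion: rate = total count / total exposure, so the ratio is multiplied by (2 − p_IFN)/(2 − p_RPC).
- Large dispersion: rate = mean of count/exposure, so the ratio is multiplied by (1 + p_RPC)/(1 + p_IFN).

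At 10%/5% these give 1.90/1.95 = 0.974 and 1.05/1.10 = 0.955. At 20%/10% they give 1.80/1.90 = 0.947 and 1.10/1.20 = 0.917.

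**Main GdE model: fits.** Maximum-likelihood negative binomial fits contained treatment and offset only. Two settings were used: GdE mean 0.6 with dispersion 2, and mean 0.3 with dispersion 4. Each used 40,000 patients per arm in four runs. The result is the ratio with the offset divided by the ratio without it on the same data (Monte Carlo SE at most 0.004).

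| Month 12 scan missed | Post-baseline scans counted | Baseline scan also counted |
|---|---|---|
| 10% / 5% | 0.966 | 0.980 |
| 20% / 10% | 0.932–0.933 | 0.960 |
| 10% / 20% | 1.073 | 1.041–1.042 |

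The first column lies between the hand limits. A separate set of fits (mean 0.4, dispersion 4) gave 0.96 at 10%/5%, moved a true ratio of 0.60 to 0.58, and gave 1.00 at 5%/5%.

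**Effect on the test.** SE of the log ratio = √[2(1/mean + dispersion)/n]. With n = 333 to 353 per arm this is 0.144–0.148 for mean 0.6 and 0.204–0.210 for mean 0.3. At 10%/5% the shift is |ln 0.966| = 0.035, or 0.16 to 0.24 SE, and a nominal 5% test becomes about 5.3% to 5.7%. At 20%/10% (|ln 0.932| = 0.070) it becomes about 6.3% to 7.8%.

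**GdE sensitivity analyses with the time offset.** Dropout time was uniform over 0.05 to 1.95 years.

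| Dropout | Mean imputation | LOCF, early-termination scan carried | LOCF, Month 12 scans only |
|---|---|---|---|
| 17% / 12% | 0.963–0.966 | 0.957–0.958 | 0.990–0.991 |
| 20% / 10% | 0.929–0.935 | 0.915–0.916 | 0.981 |
| 25% / 10% | 0.898–0.906 | 0.876 | 0.971–0.972 |
| 10% / 20% | 1.068–1.073 | 1.088–1.091 | 1.019–1.020 |

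**T2 sensitivity analyses.** Cumulative mean 4 or 8 over two years, dispersion 1.5, 200,000 per arm, one run.

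- Mean imputation with the time offset, relative to constant exposure: 0.877 and 0.852 at 20%/10%; 0.825 and 0.793 at 25%/10%. A separate set of fits (mean 5) gave 0.94 at 17%/12% with no effect, and 0.91 at a true ratio of 0.6.
- LOCF carrying the cumulative count to early termination: 0.996–1.003 with the SAP offset, but 1.05–1.09 with constant exposure. Here time on study is the right offset.
- LOCF carrying the Month 12 interval count into the missing interval: 0.965–0.978 with the SAP offset, 0.995–1.005 with constant exposure.

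The correct T2 LOCF offset therefore depends on what is carried, which the SAP does not say.

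**Equal missingness.** With no effect the factor is about 1.00. At 12% dropout in both arms and a true ratio of 0.6, the GdE time-offset factor is about 0.99.

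**The case against.** The strongest reply is that the main-model fault depends on the reading. The SAP does not define an available scan; if only the Month 24 scan is meant, the offset is log 1 and harmless. On the other reading, only missed Month 12 scans among patients with a Month 24 count matter, and the two dropout figures say nothing about those. The shift is modest, can run either way, and barely moves the type 1 error rate at 10%/5%. The observed-cases GdE analysis has nearly constant time on study, so it is in effect the model without an offset and would expose a distortion. The imputed analyses are outside the testing hierarchy. The SAP also does not say whether T2 mean imputation is per visit or cumulative.

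Most of this stands as a limit on size, and it is why the point is not more serious. It does not rescue the specification. On one reading the offset does nothing, on the other it is wrong, and on neither does it help. A sensitivity analysis is a poor safeguard for a confirmatory estimate that can be specified correctly at no cost. Some imbalance is plausible: protocol 11.1.1 holds MRI until 30 days after relapse steroids, the SAP Month 12 window closes at Day 374, and the sample size assumes that relapse rates differ by arm. That route alone is probably small.

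**Conclusion.** The specification is wrong as written and should be corrected. The offset wording fits the T2 count over 24 months but not the one-scan GdE count. The time offset does not fit values completed to Month 24 in the mean-imputed and LOCF GdE analyses or in the mean-imputed T2 analysis. Nothing in the protocol resolves this.

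The main GdE ratio moves by about 3% for a 5-point difference in missed Month 12 scans and about 7% for a 10-point difference. In the GdE imputed analyses a 10-point difference in dropout moves it by 2% to 9%, depending on which scans LOCF may carry. In mean-imputed T2 the same difference moves it by 12% to 15%. The shift favours the arm with more complete data and reverses if the imbalance reverses. All these sizes rest on assumed missingness by arm, lesion distributions and dropout timing, and on models without covariates. The mismatch itself rests on the text alone.

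The observed-cases analyses are nearly unaffected, and the scan-count offset for the observed T2 count can stay. The ratios from these models are rate ratios, not odds ratios; SAP 9.1.1 already uses the right term for the Poisson model.

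**What to change.** In SAP 9.2.1:

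- Remove the offset from the Month 24 GdE model.
- Use no offset, or one constant exposure, in the mean-imputed and LOCF GdE analyses and in the mean-imputed T2 analysis.
- For T2 LOCF, state what is carried. Keep time on study if it is the cumulative count to the last scan; use constant exposure only if interval counts are filled in through Month 24.
- Replace odds ratios with rate ratios for both lesion endpoints.

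Two smaller clarifications belong in the same edit. SAP 5.4.3 says "the last available assessment will be derived as the last value on treatment, whether scheduled or unscheduled". State whether an MRI at the early-termination visit (protocol 10.5), which follows the decision to stop treatment, counts under that rule, since the GdE LOCF shift depends on it. Also reconcile the post-steroid rescheduling of MRI (protocol 11.1.1) with the exclusion of brain MRI from visit-window extensions (protocol section 10), and state whether a scan after Day 734, the end of the SAP Month 24 window, counts as Month 24 in the analysis.

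The cost is SAP wording and minor programming, with no new data or visits. The change does not cure the understated variance of single mean imputation, so those analyses still need cautious reading.

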Efficacy and Safety of Oral RPC1063 in RMS Patients

#### Footnotes to Table 3

- 1 At Visit 1 an interim medical history will be performed to complete the screening medical history. Medical events that occur between screening and first dose will be recorded as medical history. All SAEs must be reported from the time of signing the informed consent; AEs are collected after the first dose.
- 2 Laboratory tests include Hematology, Chemistry, and Urinalysis.
- 3 Serum beta-hCG at screening, urine beta-hCG at each visit. If the urine pregnancy test is positive, do not dose and confirm with a serum pregnancy test.
- 4 Serology testing will be performed at screening to determine the patient's immune status with respect to the following viruses: Human immunodeficiency virus (HIV) antibodies, anti-hepatitis A virus IgM, hepatitis B surface antigen (HBsAg) and anti-hepatitis B core antigen (HBcAg) IgM, anti-hepatitis C virus (HCV) IgG or IgM. In addition, patients must have documentation of positive Varicella Zoster Virus (VZV) IgG antibody status or complete VZV vaccination at least 30 days prior to first dose of study medication.
- 5 The TB screening test (purified protein derivative) should be performed during the screening period and all testing must be completed prior to administration of study drug on Day 1 As available locally, an interferon gamma release assay such as QuantiFERON Gold test may be used as an alternative screening TB test or as a confirmatory test to rule out a false positive result using purified protein derivative.
- 6 Height at screening only.
- 7 A chest X-ray is not required if performed within 60 days prior to randomization and if documentation is on file.
- 8 Refer to Table 5 for details of cardiac monitoring.
- 9 RPC1063 (0.5 or 1 mg) will be administered daily for the study duration; IFN β-1a 30 μg will be administered by IM injection weekly.
- 10 Brain MRI scans will include a T2 and T1 scan (with and without Gadolinium) and will be performed at screening and then yearly.
- 11 Three MSFC practice assessments must be performed before baseline. These may be performed at the screening visit, or at any time between the screening and baseline visit.

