### 8.2.1. Extent of Exposure

Extent of exposure is defined as the total number of days a patient is exposed to any study drug. Because there is no medication diary, the extent of exposure is defined as the total number of days from the first dose date (Day 1) to the last dose date as recorded on the End of Study/Early Withdrawal page on the CRF. If the last dose date on the End of Study/Early Withdrawal page is missing or a patient is lost to follow-up, but the drug accountability log confirms that the patient has taken study drug, the visit date following the last completed drug accountability log will be used.

The extent of exposure and study drug exposure will be summarized in a table by summary statistics for the Safety Population.

The listing will present patient data for the first dose date, last dose date, extent of exposure, and study drug exposure.

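### In the mean-imputation T2 sensitivity analysis, the count is filled to 24 months but divided by a shorter exposure time, so unequal dropout alone shifts the rate ratio

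*SAP*

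**What the plan says.** The main T2 model in SAP 9.2.1 is a negative binomial regression that imputes nothing and "will include the natural log transformation of the number of available MRI scans as an offset term". Three sensitivity analyses follow:

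- The first repeats the model "using the mean number of T2 lesions from patients from the same treatment group to impute missing T2 values".
- The second repeats it "using last observation carried forward (LOCF) method for imputing missing T2 data values", with the limit that "Only data from post-Baseline MRI scans can be carried forward to subsequent timepoints for this analysis".
- The third keeps only patients whose T2 data are complete and imputes nothing.

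The offset then changes for the whole set: "All three sensitivity analyses will include the natural log transformation of exposure time on study", in place of the scan count. The same sentence recurs in SAP 9.2.1 for GdE lesions at Month 24.

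The SAP does not define exposure time on study. The nearest text is SAP 8.2.1, where "the extent of exposure is defined as the total number of days from the first dose date (Day 1) to the last dose date". Under Protocol 9.4.4.1, a patient who stops study drug has an early termination visit and one follow-up visit 4 weeks after the last dose. Protocol Table 3, footnote 10, says brain MRI "will be performed at screening and then yearly", so the scheduled post-baseline scans are at Months 12 and 24.

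**The concern.** An offset of log time turns a count into a rate, so the count and the time must cover the same period. Mean imputation extends the count to Month 24 while the denominator stops when the patient leaves. Whether exposure is read as first to last dose or as time to the last visit, it falls short of 24 months for someone who leaves early.

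These analyses are the pre-specified missing-data checks on the first-ranked key secondary endpoint. If a check can move away from 1 because of dropout alone, it may appear to confirm or to contradict the main result for a reason unrelated to lesions. The comparison is of a daily capsule with a weekly injection. The double-dummy design helps, but it does not guarantee equal dropout.

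**Working it through.** The plan states no figure for this analysis, so there is none to reproduce. Its dropout assumptions are overall figures only: about 12% (SAP 5.1) and 17% (Protocol 13.2).

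**Inputs from the documents:** about 400 patients per arm, scans at Months 12 and 24, and the imputation rules and offsets above.

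**Assumed inputs:** 4 to 8 new lesions per 24 months in both arms, dispersion about 1, non-informative dropout, and arm-specific dropout rates.

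**1. One patient, mean imputation.** Let m be the expected 24-month count and T the months of exposure. The modelled rate is m/T and the true rate is m/24, so the inflation factor is 24/T.

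- T = 6: 24/6 = 4.0
- T = 12: 24/12 = 2.0
- T = 18: 24/18 = 1.33
- T = 21: 24/21 = 1.14

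**2. One patient, LOCF from the Month 12 scan.**

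- Per-interval counts: m/2 is observed and m/2 is carried forward, so the total is m and the factor is again 24/T (2.0 at Month 12, 1.33 at Month 18).
- Cumulative counts: the carried total is m/2, so the factor is 12/T (1.0 at Month 12, 0.67 at Month 18). There is no inflation.
- No post-baseline scan: no value is carried.

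**3. Rate ratio by hand.** Suppose a fraction d of an arm leaves at Month 12, under mean imputation. Total count over total exposure inflates the arm rate by 1/(1 − d/2). An equally weighted mean of patient rates inflates it by 1 + d. A negative binomial fit should fall between these.

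- 24% versus 12%: (1 − 0.12)/(1 − 0.06) = 0.936, and 1.12/1.24 = 0.903.
- 17% versus 12%: (1 − 0.085)/(1 − 0.06) = 0.973, and 1.12/1.17 = 0.957.

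Earlier departures enlarge the shift. If leaving is uniform from Month 1 to Month 24, the mean of 24/T is (24/23) × ln 24 = 3.32. The equal-weight limit at 17% versus 12% is then (1 + 0.12 × 2.32)/(1 + 0.17 × 2.32) = 1.278/1.394 = 0.917.

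**4. Simulation with no true effect.** There were 300 trials per row, 400 per arm, 4 lesions per 24 months, dispersion 1 and no covariates. Entries are rate ratios, RPC1063 over IFN β-1a.

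| Dropout IFN / RPC1063 | Leaving time | Mean imputation, exposure offset | Same data, constant offset | LOCF per interval | LOCF cumulative | Observed cases | Main T2 model |
|---|---|---|---|---|---|---|---|
| 12% / 12% | Month 12 | 0.993 | 0.993 | 0.993 | 0.993 | 0.993 | 0.993 |
| 17% / 17% | Months 3–24 | 0.992 | 0.994 | 0.994 | 0.993 | 0.994 | 0.993 |
| 24% / 12% | Month 12 | 0.917 | 1.008 | 0.918 | 1.009 | 1.008 | 1.009 |
| 24% / 12% | Months 3–24 | 0.901 | 0.998 | 0.969 | 1.022 | 0.999 | 0.997 |
| 7% / 17% | Months 3–24 | 1.086 | 0.995 | 1.019 | 0.977 | 0.994 | 0.996 |

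At 24% versus 12%, mean imputation with the exposure offset rejected at the nominal 5% level in 23% (Month 12) and 32% (Months 3–24) of trials. The same data with a constant offset rejected in about 5%.

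**5. Wider assumptions.** Across 4 to 8 lesions and different leaving times, the mean-imputation ratio was about 0.86 to 0.92 at 24% versus 12% and 0.92 to 0.96 at 17% versus 12%. A constant offset gave 0.99 to 1.01. By step 3, the low end at 17% versus 12% needs early departures.

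**The case against.** A reader might infer more than the documents support, in four ways.

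- **All three analyses are wrong.** The quoted sentence covers all three, but the observed-cases analysis imputes nothing and excludes patients without complete data. Its exposure offset is nearly constant, and its null ratio stays at about 1.
- **Every dropout's rate is inflated.** This is not so under LOCF. A patient without a post-baseline scan gets no value, and cumulative counts are not inflated. Protocol Table 4 also schedules a brain MRI at early termination. If that scan supplies a cumulative count to carry forward, count and exposure end at about the same time and the exposure offset is right. The windows in SAP 5.4.3 leave its use unclear. A patient who misses a scan but stays in the study keeps full exposure and is not inflated either.
- **Dropout as such creates a treatment effect.** Equal dropout with similar timing cancels in the ratio. Arm-level rates are still raised, but the SAP reports between-arm ratios (labelled odds ratios) and relative reductions for this endpoint.
- **The confirmatory test is compromised.** The test in the SAP 5 hierarchy uses the main T2 model, which has the scan-count offset and no imputation.

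It is also fair to say that the documents give no arm-specific dropout, lesion rate or dispersion, and no definition of exposure time on study. The sizes above are therefore illustrations. What survives is the mean-imputation analysis: no reading of the offset found in the SAP gives a patient who left early 24 months of exposure.

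**Conclusion.** The point holds for the mean-imputation analysis, and conditionally for LOCF. As written, the mean-imputation analysis divides a 24-month count by a shorter time, and a difference in dropout between arms biases the ratio towards the arm with less dropout, whichever arm that is. Using the plan's two overall dropout figures as if they were arm rates (17% versus 12%), the spurious shift is about 4% to 8%. At 24% versus 12% it is about 8% to 14%.

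LOCF with per-interval counts gives about 0.97 at 24% versus 12% when departures are spread over the study. It matches the mean-imputation shift only if everyone leaves just after the Month 12 scan.

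The consequence is limited to robustness checks: no alpha and no gated claim is affected. The mechanism follows from the SAP text. The sizes depend on the assumed lesion rate, dispersion and dropout pattern. The GdE analyses were not quantified here.

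**What to change.** In SAP 9.2.1:

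- For T2 sensitivity analyses whose counts are imputed to 24 months, replace the exposure-time offset with a constant (log of 2 years) or use none.
- Keep an exposure-type offset only for unimputed counts, measured from baseline to the last T2 scan, and define it. The observed-cases analysis needs no offset, because its patients share the same scan interval.
- State whether LOCF carries per-interval or cumulative counts, and whether an early-termination scan can be carried forward. Then choose the matching offset.
- Review the identical offset sentence for GdE lesions at the same time.

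The cost is a few SAP sentences and a programming change. No new data are needed. It should be done before database lock.
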